## **Proposed Procedures/Methodology**

### **2.3.5 clinical evaluation**

- Demographic and clinical characteristics: An initial assessment will be carried out, where personal data and clinical history will be collected.

### **2.3.6 Peripheral Muscle Assessment**

#### **2.3.6.1 Palm grip dynamometry**

Traditionally, handgrip strength (HGS) tests have been used in rehabilitation to assess the physical condition of the upper limbs, by measuring the strength of the hand and forearm muscles of patients with various disorders in the upper extremity resulting from arthritis, rheumatoid disease , carpal tunnel syndrome, lateral epicondylitis , stroke, traumatic injuries, myopathy , ICU-acquired muscle weakness, critical patient polyneuropathy and neuromuscular diseases (INNES E, 1999; KURILLO GA *et al* ., 2004; MOREIRA D *et al.*, 2004; MOREIRA D *et al.* *al* ., 2003) HGS measurement by

dynamometry presents a good correlation with the functional level of the upper limbs and general health status, being widely used in the selection of therapeutic procedures and monitoring of functional rehabilitation (INNES E, 1999). Manual dynamometry has wide applicability, as it is a low-cost, simple, fast and non-invasive method (GÜNTHER CM *et al.*, 2008) that provides, through HGS values, an indicator of the general health of the evaluated individuals.

The HGS assessment will be performed by a single previously trained investigator, in the morning between 8 am and 12 noon, according to the recommendations of the Brazilian Society of Hand Therapists (SBTM, 2008). The individuals will be positioned seated with the arm adducted parallel to the trunk, shoulder in neutral rotation, elbow flexed at 90°, forearm in fundamental position. Wrist hyperextension of up to 30° and ulnar deviation of up to 15° will be allowed during the tests. Three measurements will be taken from both hands, with a minimum interval of 30 seconds between them. The tests will be performed alternately between the dominant and non-dominant side, to minimize the influence of muscle fatigue. For data analysis, the highest value obtained for each hand will be considered. The dominant hand is defined as the preferred hand for carrying out daily activities. Volunteers will be asked which hand they prefer to carry out activities such as writing, eating and carrying objects. During the execution of the handgrip, the arm will remain immobile, with only permission for the movement of the wrist and finger joints.

Will be used as prediction formulas (NOVAES RD *et al.*, 2009):

- $HGS-D,_{kgf} = 39.996 - (0.382 \times age,_{years}) + (0.174 \times weight,_{kg}) + (13.628 \times sex \text{ (men=1; women=0)})$
- $HGS-ND,_{kgf} = 44.968 - (0.420 \times age,_{years}) + (0.110 \times weight,_{kg}) + (9.274 \times sex \text{ (men=1; women=0)})$

### **2.3.6.2 Quadriceps Maximum Load Test**

The one-repetition maximum test (1RM) is often used as a measure of muscle strength, whether in the context of physical rehabilitation. In this sense, there is a consensus that the basis for prescribing therapeutic exercises, especially those

performed against resistance TCR) is established through the relationship between the percentage of 1RM and the number of repetitions.

The 1 RM Test will be performed in an extension chair, with adjustments that keep the hip and ankle flexed at 90° and the knee flexed to ensure an angular trajectory of 120° after extension. The 1RM tests will be conducted according to the protocol proposed by Brown and Weir (Brown & Weir, 2001). Before each test, free, light activities involving the tested muscle will be performed, followed by 1 min of stretching for the tested muscle ( in this case, the quadriceps will be tested). After stretching, 3 repetitions were performed with moderate load and after 5min of rest and interval, the 1RM test will be performed, adding weights when necessary, 0.4 to 5kg, totaling up to five attempts. We will record the maximum load as the greatest load lifted in a single movement of full knee extension in an open kinetic chain.

For the reference values, the highest value among the three measures of maximum voluntary contraction in the 1RM test, normalized by the body weight of each individual tested, was used, according to the formula proposed by Magalhães in 2010:  $(\text{Strength (Kg)} / \text{Weight} \times 100)$

### **2.3.6.3 Quadriceps Muscle Endurance Test**

The quadriceps muscular endurance test will be performed after 30 min of rest after the 1 RM test. We will use a load of 40% of the load obtained in the 1 RM test, rounding up to the next higher load in case of load fractions.

The muscular endurance test will be performed in the same extension chair, with hips, ankle at 90° and knee flexed to ensure an angular velocity of 1'20°/s using the dominant lower limb ( LLd ). Volunteers will be instructed to count 1 second for LL extension and 1 second to return to flexion (angular velocity of 120°/s). The outcome of this test will be the time to exhaustion characterized by failure or inability to complete the range of motion.

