#### *maximum voluntary contraction*

[figure not shown]
The assessment of muscle strength and endurance can be obtained by maximal voluntary contraction (MVC). This assessment can be done by instructing the patient to generate as much voluntary force as possible without altering muscle length (symmetrical test) or by encouraging the patient to perform a full range of motion with the greatest possible load (1RM test). In this evaluation, equipment such as tensiometers or dynamometers can be used to quantify the generated isometric force (if there is no change in muscle length). In the case of the 1 RM test, the highest load imposed and that the patient can complete and repeat is considered. As these are volitional techniques, external complicating factors, such as the patient's functional ability and motivation, can generate submaximal contractions and thus underestimate the analysis. However, due to the ease of execution, verbal encouragement and technical experience, little variability has been described in our tests involving maximal voluntary contraction (MVC). In patients with chronic pulmonary dysfunction, the loss of the ability to generate or maintain MVC during knee extension exercise has been representative of muscle fatigue. (SWALLOW EB *et al.*, 2007). Studies have used series of submaximal voluntary contractions in the evaluation of resistance and peripheral muscle fatigue. Usually, relative values of approximately 20-60% of MVC (1RM test or isometrically sustained maximal voluntary contraction ) are required to be sustained until exhaustion, maintaining cadence and rhythm constant or close to it. Resistance is measured by the time the task is maintained. The test should be stopped

when there is a failure to maintain the intensity of the contraction (5% drop) or inability to complete the range of motion or visually there are signs of muscle fatigue, such as fasciculations , for example.

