### *Pilates training principles*

**Concentration** : Pilates training requires a mental focus on the target area of the body itself. Concentration draws attention to the working body segment, potentially improving functioning and, ultimately, improving the quality of movement (MUSCOLINO JE *et al.*, 2004).

*Control* : Pilates training is aimed at contracting the right muscle at the right time so that proper movement can take place. Each stage from start to finish of the movement continues and ends under control. Controlled movement also reduces the risk of injury (IULIAN-DORU T *et al.*, 2013).

*Centering* : There are many muscles in the abdomen, lumbar region and hip complex, which is accepted as the center of our body and called the central region. Muscles such as the multifidus , quadratus lumborum, iliopsoas , transversus abdominis, and diaphragm in this are primarily involved in protecting the lower back. One strong and active core is an indication of a strong center. With centralization, movements of the head, shoulders, chest, pelvis and extremities are organized around a central base (MUSCOLINO JE *et al.*, 2004; IULIAN-DORU T *et al.*, 2013).

*Fluency* : In Pilates training , the flow of movements is continued with a mind-body interaction. Movements and transitions must occur in a slow, fluid harmony to best achieve the training effects. Breathing and concentration are also included in this adaptation process (WOOD S, 2018).

*Precision* : Pilates training is concerned with quality, not quantity. Perform the movements correctly instead of repeating a certain one sometimes increases the quality of movement. Activation and contraction of target muscles at the target time depends on this. In cases where this principle is not enough, training moves away from the integrity within itself (UNGARO A, 2011).

*Breathing* : It is important to breathe properly during exercise. Breathing is believed to be a catalyst for core stability. Compared with other exercise methods, diaphragmatic breathing is used less in Pilates (LEMOS AQ *et al.*, 2019)

*training* . The reason for this is the view that increased intra-abdominal pressure during diaphragmatic breathing reduces transversus abdominis muscle activation (MUSCOLINO JE *et al.*, 2004).

*Integrated Isolation* : To learn correct posture and maximize the benefit to be gained from movement, daily activities must be continued within the framework of centering and other principles (LATEY P, 2001)

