## **2.3 Sample**

The sample will consist of 60 participants, divided into two groups: an intervention group (n=30) that will do a 12-week program, 2x/week of Pilates method exercises , and a control group (n=30) that will not do any intervention for rehabilitation in the period.

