## 2.4 Outcomes

### 2.4.1 primary outcome

As variables for the primary outcome of this research, it will be the functional performance, resulting from the combination of the PCFS Scale with the Dynamometry of Pressure Para, Test of Strength and of Endurance of the quadriceps muscle.

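### Quadriceps endurance, a primary-outcome component, is timed at a pace the volunteer counts alone, so slowing can lengthen the score and the procedure specifies no check on pace

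*Combined protocol and SAP*

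**What the plan says.** Section 2.4.1 builds the primary outcome from four measures: the PCFS scale, grip dynamometry, and the "Test of Strength and of Endurance of the quadriceps muscle".

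Section 2.3.6.3 describes the endurance test.

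- **Load:** "We will use a load of 40% of the load obtained in the 1 RM test".
- **Pace:** "Volunteers will be instructed to count 1 second for LL extension and 1 second to return to flexion", which the section equates to 120°/s.
- **Score and end point:** "The outcome of this test will be the time to exhaustion characterized by failure or inability to complete the range of motion".

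The section mentions no metronome, no check of pace by the assessor, no tolerance for drift, no stop for loss of pace and no repetition count. The budget table lists a stopwatch but no pacing device.

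The background text on maximum voluntary contraction (section 1.1.9.4) describes tests of this type differently. Submaximal loads "are required to be sustained until exhaustion, maintaining cadence and rhythm constant or close to it". There the stop criteria are a 5% fall in contraction intensity, an incomplete range of motion, or visible signs of muscle fatigue.

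**The concern.** The score is elapsed time, but the person being tested controls how fast the repetitions go. With the load and range fixed, mechanical work is proportional to the number of repetitions. The stopwatch rewards seconds, whether they come from more repetitions or from slower ones. Someone who stretches the count, or pauses between repetitions, can therefore gain time without doing more work. Because repetitions are not recorded, no later analysis could separate endurance from pacing.

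Two things are at stake.

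- **Precision.** Differences in pace between patients, and between the two visits of one patient, add noise to a primary component.
- **Comparability of the arms.** The background lists slow movement as a Pilates principle ("Movements and transitions must occur in a slow, fluid harmony to best achieve the training effects"), while the comparator is "a control group (n=30) that will not do any intervention for rehabilitation in the period". If training changed how people pace a counted task, the arms could differ in seconds without differing in endurance.

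Section 2.2 bases its blinding claim on the volunteers and the Pilates professional. It does not name a blinded outcome assessor who might hold the pace.

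**Working it through.** **1. Is there a plan figure to reproduce?** None for endurance time: the protocol gives no expected value, standard deviation or important difference for it. The only sample-size calculation (section 2.5.1) uses maximum load: d = 4.7/5.05 = 0.93, two-sided α = 0.05, power 0.80. It reproduces: n = 19.16, rounded up to 20, and 20 × 1.2 = 24 per group. It does not bear on the endurance score.

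**2. The two descriptions side by side.**

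| Feature | Background, 1.1.9.4 | Trial procedure, 2.3.6.3 |
|---|---|---|
| Cadence | constant or close to it | 1 s up, 1 s down, counted by the volunteer |
| Stop: intensity | 5% drop | not stated |
| Stop: range | incomplete range | incomplete range |
| Stop: visible fatigue | yes | not stated |
| Score | time the task is maintained | time to exhaustion |

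**3. How far can pace move the score?** The planned cycle is 2 s. Let the actual cycle be c seconds, and let f be the share of fatigue incurred per repetition, the rest being incurred per second of effort. Relative to the planned pace:

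- repetitions completed = 1 / [f + (1 − f)·c/2]
- time score = (c/2) / [f + (1 − f)·c/2]

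Both c and f are assumptions, because the documents give neither.

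| Cycle | f = 0 (per second only) | f = 0.25 | f = 0.5 | f = 1 (per repetition only) |
|---|---|---|---|---|
| 2.5 s | 0% | +5% | +11% | +25% |
| 3.0 s | 0% | +9% | +20% | +50% |

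Example at c = 2.5 and f = 0.5: 1.25 / (0.5 + 0.5 × 1.25) = 1.25/1.125 = 1.11. Taking 30 repetitions at the planned pace for illustration, the score is 30 × 2 = 60 s. Slowing gives 30/1.125 = 26.7 repetitions × 2.5 s = 66.7 s. The score rises 11% while the work done falls 11%. At f = 1 the same patient scores 30 × 2.5 = 75 s, or 30 × 3 = 90 s. These last two values are ceilings.

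In this model slowing never shortens the time. Rest taken during pauses is not modelled.

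**4. What if the drift were confined to one arm?** Suppose pacing alone lengthens the mean time by 10% in one arm, with no true gain in endurance, and the coefficient of variation (CV) of endurance time is 0.3 to 0.6. All of these are assumptions. Then d = 0.10/CV, which is 0.33 down to 0.17. A two-sided 5% two-sample t-test on this component would be significant in:

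- 20% down to 9% of trials at 24 per group (section 2.5.1);
- 25% down to 10% of trials at 30 per group (section 2.3).

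The planned mixed-design model also uses baseline values, so these figures show only the order of magnitude.

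**The case against.** The strongest reply is that the protocol does prescribe a pace, so drifting or pausing departs from the procedure and what is missing is only enforcement. Part of that stands: the intended cadence is clear. But in a test scored in seconds and paced by the person tested, enforcement is part of the measurement.

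It can also be said that failure, in the definition of exhaustion, may mean more than loss of range and may abbreviate the background's list of stop criteria. That reading is possible, so it would be wrong to say that only loss of range can end the test. Even so, neither place states a rule for loss of pace.

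A reader might infer that Pilates itself inflates the score and that the trial is biased towards benefit. The documents do not support this, for three reasons.

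- The slow-movement principle comes from a general account of the method. The trial's exercise protocol (section 2.3.11) sets no tempo, and section 1.2 also speaks of working muscles at the correct speed. Trained patients might keep the count better, while untrained controls might slow as they tire.
- The test load is a percentage of the 1RM. If the 1RM is re-measured at follow-up, a patient who has grown stronger faces a heavier load, which could shorten the time and work against Pilates.
- No document gives a figure for drift in either arm.

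Finally, endurance is one of four components and did not drive the sample size. That limits the weight of the point but does not remove it.

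**Conclusion.** The point holds as a measurement weakness in a primary-outcome component. The written procedure lets pace enter a time score, contains no stated means of detecting it, and is looser than the protocol's own description of such tests.

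The possible distortion is 0% to +25% at a 2.5 s cycle and 0% to +50% at 3 s. Where it falls depends on whether fatigue accrues per second or per repetition, and the drift itself is assumed. Added measurement error is the expected consequence. Bias between the arms is a plausible risk, with neither direction nor size established. A positive endurance result would be hard to interpret cleanly, but it cannot be called spurious on this ground.

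The change should be made before baseline testing, because pace and repetitions cannot be recovered afterwards.

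**What to change.** Amend section 2.3.6.3 as follows.

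1. Pace the test with an external metronome at the stated 1 s up and 1 s down.
2. End the test at the first of incomplete range of motion or failure to keep the beat under a pre-specified tolerance. Two consecutive missed repetitions after one verbal cue would be one example; the exact tolerance is for the investigators to set.
3. Keep time as the score and also record completed in-pace repetitions. With the beat held, time should equal about 2 s × repetitions, so the count serves as a check on pacing and need not replace the outcome.
4. Apply the same rule to both arms at both visits.
5. Reconcile the stop criteria with those in section 1.1.9.4, and state what failure means.

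The cost is a free metronome application and a few sentences in the procedure. The downside is that times may be somewhat shorter than under self-pacing and less comparable with self-paced tests elsewhere.

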### **2.3.7 Post COVID functional scale (PCFS)**

The Post-COVID-19 Functional Status Scale is a longitudinal patient assessment tool for identifying changes in post-COVID-19 functional status and their evolution. The PCFS scale covers the entire set of functional areas, in particular limitations in activities of daily living (ADL) and in the workplace, as well as changes in lifestyle. The scale can be administered to the patient by trained staff or conducted by the patient as a self-assessment. In the project, following the guidelines of the PCFS, which will be used for research purposes, it will be conducted by a trained evaluator and followed all the guidelines described for this purpose. This scale consists of six ordinal categories that reflect conditions of increasing severity, from 0 to 4. Death is coded as "D". Grade 0 implies the absence of any residual symptoms. If one or more residual symptoms are present but do not affect the patient's normal activities, grade 1 will be assigned. If they are limited in intensity/frequency or occasionally avoided, grade 2 will be assigned; grade 3 implies limitations that force the patient to reprogram usual activities, reflecting the inability to perform some of them, which, in fact, must be performed by others. Grade 4, the most severe, is reserved for severe functional restrictions that require continuous assistance in daily activities (CORSI *et al.*, 2020; KLOK *et al.*, 2020) .

### **2.3.8 Dyspnea assessment by the modified Medical Resource scale Council ( mMRC )**

*medical resource modified dyspnea scale council ( mMRC )*: consists of only five items, and the patient chooses the item that corresponds to how much dyspnea limits their ADLs . The patient reports his subjective degree of dyspnea by choosing a value between 0 and 4, where 0 (suffers from shortness of breath only during intense exercise), 1 (suffers from shortness of breath when walking quickly, climbing stairs or ramps), 2 (walks slower than people of the same age because of shortness of breath or having to stop for breath even when walking slowly), 3 (to breathe after walking less than 100 m or after a few minutes) and 4 (feel so short of breath who doesn't leave the house anymore, or I need help dressing or bathing alone) (ANNEX 1). The mMRC dyspnea scale showed satisfactory reliability and validity (KOVELIS *et al.*, 2008) .

For the perception of effort during the exercises of the intervention group, the modified Borg scale will be used : which is a subjective scale to qualify the degree of

respiratory distress during exercise, where option 0 means no effort and 10 means maximum effort and will be used exclusively during Pilates sessions to control exercise intensity.

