We have the modified Borg scale , which is characterized by being a subjective scale, adapted by BURDON, in 1982, to measure dyspnea both during exercise or in physical activities, since the measurement is made directly at the moment of that the patient is experiencing the sensation (BORG, 1998). The Borg scale seeks to assess the subjective sensation of exertion (also described as a sensation of respiratory fatigue), and covers a score from 0 to 10, where: 0 means no respiratory difficulty, while 10 represents maximum respiratory difficulty.

Because it is an extremely subjective scale, over time, and in order to allow a better understanding of the perceived exertion by the evaluated individual, the insertion of quantitative expressions of intensity was established so that there was a direct correlation between the numerical categories. and verbal descriptors (HIGBEE, DODD, 2020, SILVA, DIAS, *et al.* , 2011) . It is worth mentioning that the Borg scale includes instructions for its use, together with the structure to be evaluated, seeking not only to facilitate the individual's understanding, but above all to increase the accuracy of the response in relation to the subjective perception of effort during the proposed activities (CABRAL , LOPES, *et al.* , 2017, GOMES, SHUJMAN, *et al.* , 2019, LIMA DE, MAGALHÃES, *et al.* , 2019) .

The assessment of dyspnea in relation to limitations in performing routine activities requires some intersection between uni and multidimensionality, so that it is possible to quantify it. In this context, the most cited scale in the literature is the Modified Scale of the British Medical Research Council ( *MMRC - Modified Medical Research Council* ), created by English pulmonologists in 1960, and since then it has

been used to measure breathing difficulty in ADLs (activities of daily living) and perceived respiratory incapacity (BESTALL *et al.* , 1999, DA CAPITAL *et al.* , 2018).

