### **2.3.4 Risks and Benefits**

The possible risks of this research are, the increase in the sensation of shortness of breath during the execution of the exercises, the reduction of the saturation of O2 and, the possible muscular pains resulting from the practice of the Pilates Method .

As benefits we can mention: the improvement of the disposition to carry out the activities of daily living, the improvement of the balance, in addition to obtaining gains in relation to the quality of life and the reduction of dyspnea.

The research will be immediately suspended if any risk or damage to the health of the subject participating in the research is perceived, resulting from it, not provided for in the consent form (ICF). If it is proven that a group has benefited from the intervention of the protocol of this work, the same intervention will be offered to the other group, avoiding any harm to the patient.

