**Table 3: Budget details.**

Budget identification	Type	Price R\$)
Physiotherapist specializing in Pilates	execution team	BRL 0.00
reformer	permanent material	BRL 0.00
Cadillac	permanent material	BRL 0.00

Chair	permanent material	BRL 0.00
Lader barrel	permanent material	BRL 0.00
pulse oximeter	permanent material	BRL 0.00
stopwatch	permanent material	BRL 0.00
palm grip dynamometer	permanent material	BRL 0.00
Extension chair and load cell	permanent material	BRL 0.00
Video camera	permanent material	BRL 0.00
Reproduction of evaluation sheets	Material consumption	BRL 50.00
A4 paper format	Material consumption	BRL 50.00
	Total in BRL	BRL 100.00

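### The Borg scale has conflicting anchors and is confined to Pilates sessions, so a listed dyspnea outcome has no control-arm data; the reason an endurance test ended and the use of the listed oximeter are not stated.

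*Combined protocol and SAP*

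**What the plan says.** Four parts of the protocol bear on this point.

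- **Risks (2.3.4).** The named risks are "the increase in the sensation of shortness of breath during the execution of the exercises, the reduction of the saturation of" oxygen, and "the possible muscular pains resulting from the practice of the Pilates Method".
- **Borg scale.** Section 2.3.8 introduces the modified Borg scale as a rating of perceived effort for the intervention group. It then describes the scale as grading breathing difficulty, "where option 0 means no effort and 10 means maximum effort and will be used exclusively during Pilates sessions to control exercise intensity". The background in 1.1.9.2 gives other anchors for the scale: "0 means no respiratory difficulty, while 10 represents maximum respiratory difficulty". Section 2.4.2 lists Borg with mMRC as a measure of reduced dyspnea.
- **Strength and endurance tests.** Section 2.3.6.2 describes a one-repetition maximum test with up to five attempts. Section 2.3.6.3 describes an endurance test at 40% of that load: "The outcome of this test will be the time to exhaustion characterized by failure or inability to complete the range of motion". Quadriceps strength and endurance are both components of the primary outcome in 2.4.1.
- **Equipment.** Table 3 in section 2.7 lists a "pulse oximeter" at BRL 0.00. The supplied procedures, 2.3.5 to 2.3.11, do not mention it.

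**The concern.** Two outcomes and one safety observation are affected.

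First, a secondary outcome needs scores from both arms, and the rule in 2.3.8 produces them in one arm only. Even in that arm, the text does not settle whether the score measures effort or breathing difficulty.

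Second, the endurance time is meant to reflect the quadriceps. If a test were ended by a symptom, the plan would record it in the same way as leg failure, and nothing in the data would show the difference. That matters because the time enters the primary outcome.

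Third, the protocol foresees a fall in saturation and lists a device that measures it, but no supplied procedure connects the two. If no readings are recorded, the trial cannot say whether the foreseen event occurred.

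**Working it through.** The plan gives no figure of its own on this point. The check sets the sections side by side and then counts occasions.

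**1. What Borg measures.**
- 2.3.8, stated purpose: perceived effort.
- 2.3.8, description: breathing difficulty during exercise.
- 2.3.8, anchors: no effort to maximum effort.
- 1.1.9.2, anchors: no to maximum respiratory difficulty, although the same sentence also speaks of exertion.
- 2.4.2, role: dyspnea outcome.

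The sections do not give one construct. With effort anchors, a high score could come from tired legs or from breathlessness.

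**2. Who has Borg data.** Under 2.3.8 the scale is used *exclusively* in Pilates sessions. Under section 2.3 the control group has no rehabilitation intervention during the period. Control patients with a Borg score are therefore 0 of 24 (group size in 2.5.1) or 0 of 30 (group size in 2.3). Section 2.5.5 plans a comparison of the Pilates and control groups on all variables in each period. For Borg that comparison cannot be made.

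**3. How the endurance test ends.** The end point in 2.3.6.3 is failure or an incomplete range of motion. No reason for ending is recorded. The background in 1.1.9.4 mentions ending such a test at a 5% drop in contraction intensity, lost range of motion or visible muscle fatigue. None of these is respiratory, and none separates a symptom from leg failure.

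**4. Where saturation is read.** No saturation reading is stated in 2.3.6.2 (maximum load), 2.3.6.3 (endurance) or 2.3.11 (sessions). The suspension sentence in 2.3.4 is general and names no measurement.

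**5. Scale.**
- Group size: 2.5.1 uses d = 4.7 / 5.05 = 0.93 and obtains n = 19.159 per group. This reproduces with a two-sided t-test at alpha 0.05 and power 0.80. Rounded up it is 20, and 20 × 1.2 = 24 per group, or 48 in all, as in the Summary. Section 2.3 instead gives 30 per group, 60 in all. Both are carried as a range.
- Sessions per patient: 12 weeks × 2 = 24.
- Participant-sessions at full attendance: 24 × 24 = 576, or 30 × 24 = 720.
- Participant test visits, before and after in both arms: 48 × 2 = 96, or 60 × 2 = 120.

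These counts show how many occasions have no stated saturation reading. They measure neither harm nor bias.

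**The case against.** **Consent form.** The ethics checklist in Appendix 2 places precautions against adverse effects in the consent form, and those pages were not available. Monitoring may be described there. This stands, and it limits the oximeter point to the supplied text.

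**Oximeter.** A reader might infer that it is never used, or that zero readings are planned. The documents do not support that. Table 3 also lists a stopwatch, which the procedures do not name although timing to exhaustion needs a timer. The procedures are not a full equipment list, and listing the oximeter suggests some intended use. What can be said is that its use is not described.

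**Borg wording.** Section 1.1.9.2 itself mixes exertion with breathing, and the text reads as a translation, so much weight on one word would be unsafe. This stands. The point is an inconsistency to reconcile, not a correct section broken by a wrong one. Nor is the trial left unable to measure dyspnea: mMRC is collected before and after in all patients.

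**Tests.** A reader might infer that the tests are the most strenuous tasks, or that breathlessness will end them. Neither is shown. These are seated knee extensions with rest periods, the endurance test uses one limb, and 2.3.4 links breathlessness to performing the exercises. The endurance point is therefore conditional.

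**Safeguards.** Patients on home oxygen are excluded, entry is at least 90 days after discharge, and a specialised physical therapist treats at most 3 patients at a time. These are relevant to risk, but they do not supply control-arm Borg data or a reason for ending a test.

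**Conclusion.** The point holds in this form. The firmest part follows from the stated rules: Borg is a listed secondary outcome with no control-arm data, so it cannot be compared between arms, and its anchors conflict across sections. The endurance part holds as a gap in recording. A symptom-limited test, if one occurs, cannot be told from quadriceps failure in a component of the primary outcome. The documents give no frequency for such tests, so the size of any misclassification is unknown. The oximeter part holds for the supplied text: a named risk and a listed device, with no described use across up to 576 to 720 participant-sessions and 96 to 120 test visits. Those counts assume full attendance and both assessments in every patient.

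A reader might go further and conclude that the trial would report an absence of desaturation. No supplied section plans such a report, so this does not follow. The primary comparison is not invalidated.

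**What to change.** 1. Reconcile 1.1.9.2, 2.3.8 and 2.4.2 on what Borg measures and how it is anchored. Then either lift the restriction to Pilates sessions for the outcome measure, so that dyspnea is scored at the before and after test visits in both arms, or remove Borg from the outcomes in 2.4.2 and rely on mMRC.
2. In 2.3.6.3, record why each endurance test ended: leg failure or a symptom, and which symptom.
3. Reconcile 2.3.4, 2.3.6.2, 2.3.6.3, 2.3.11 and Table 3 of 2.7 by stating where the listed oximeter is used and recording its readings at sessions and tests. The timing of readings, any limits and any action on them are for the responsible clinicians to set.

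The cost is a few more form fields and some extra readings for one therapist with up to 3 patients. The oximeter is already listed at zero cost.
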